3.2 DISCUSSION OF TRIAL DESIGN, INCLUDING THE CHOICE OF CONTROL GROUP(S)

This is a randomized double blind, placebo controlled, parallel design study. This design is appropriate for assessing the safety and efficacy of BI 655066 compared to placebo in patients with moderate to severe chronic plaque psoriasis. While there is a low rate of response with placebo treatment, it is important to have a placebo control early in the study to control for confounding factors, such as potential investigator bias or regression to the mean in PASI scoring.

In order to enroll patient participants, it is necessary to allow patients initially assigned to placebo to receive active treatment. Thus, only adverse events reported during the first 16 weeks of the trial can be directly compared to placebo. In this trial, patients originally randomized to BI 655066 who are considered to be BI 655066 responders will be re-randomized to receive either placebo or continued BI 655066 starting at Week 28. Patients in this phase of the study will be assessed for an additional 76 weeks for a total of 104 weeks. This is necessary to adequately capture the loss of response for patients taking BI 655066. Furthermore, patients losing response will be retreated with BI 655066 and response after retreatment will be assessed.

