7.3.4 Safety analyses

Adverse events will be coded using the Medical Dictionary for Drug Regulatory Activities (MedDRA) coding dictionary. Standard AbbVie summary tables and listings will be produced. All adverse events with an onset between start of treatment and end of the residual effect period (REP), a period of 15 weeks days after the last dose of trial medication, will be assigned to the treatment period for evaluation.

All treated patients will be included in the safety analysis. In general, safety analyses will be descriptive in nature and will be based on AbbVie standards. No hypothesis testing is planned.

Statistical analysis and reporting of adverse events will concentrate on treatment-emergent adverse events. To this end, all adverse events occurring between start of treatment and end of the residual effect period will be considered 'treatment-emergent'. Adverse events that start before first drug intake and deteriorate under treatment will also be considered as 'treatment-emergent'.

Frequency, severity, and causal relationship of adverse events will be tabulated by system organ class and preferred term after coding according to the current version of the Medical Dictionary for Drug Regulatory Activities (MedDRA).

Laboratory data will be analysed both quantitatively as well as qualitatively. The latter will be done via comparison of laboratory data to their reference ranges. Values outside the reference range as well as values defined as clinically relevant will be highlighted in the listings.

Treatment groups will be compared descriptively with regard to distribution parameters as well as with regard to frequency and percentage of patients with abnormal values or clinically relevant abnormal values.

Vital signs, physical examinations, or other safety-relevant data observed at screening, baseline, during the course of the trial and at the end-of-trial evaluation will be assessed with regard to possible changes compared to findings before start of treatment.

More information on the analysis of safety will be given in the TSAP.

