10.1.2 Analyses of Continuous Variables

For continuous variables, the model based mean and standard error will be presented. The Baseline and visit means will also be presented for each treatment group for subjects who have both Baseline and post Baseline visit values. The treatment groups will be compared using ANCOVA with treatment group, Baseline value, and stratification factors in the model.

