11.0 Safety Analysis

11.1 General Considerations

Safety analyses will include adverse events, laboratory, local tolerability, ECG, and vital sign measurements. Safety summaries will be provided using the safety population in each period as defined in Section 5.1. Comparison between risankizumab group and placebo group will be performed in the Safety Population in Safety_A1 and Safety_B_R populations. Continuous variables will be analyzed using one-way ANOVA and

categorical variables will be analyzed using Fisher's exact test. For analyses of AEs, only P values ≤ 0.100 when rounded to three digits will be presented.

Missing safety data will not be imputed.

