11.3.2 Statistical Methods

Analysis of Quantitative Laboratory Parameters (Hematology and Chemistry)

Though the protocol indicates utilizing the Rheumatology Common Toxicity Criteria (RCTC) scale for grading laboratory values, given that the National Cancer Institute Common Toxicity Criteria for Adverse Events (NCI CTCAE) scale includes a more comprehensive list of laboratory values; the lab analyses based on the NCI CTCAE scale will be presented. Changes from Baseline to each scheduled visit and to the final value in continuous laboratory parameters will be summarized with the mean, standard deviation and median. The Baseline and visit/final value means will also be presented for subjects who have both the Baseline and visit/final values (see Section [6.0](#) for the definition of Baseline and final values).

If there are multiple post-baseline measurements on the same day, average value will be used.

Shift Tables

Shift tables for changes from Baseline according to the normal range will be provided for each hematology, and clinical chemistry parameter. Shifts from Baseline to the following endpoints will be considered: minimum value, maximum value and final value. Categories of "low or normal" and "high or normal" will be included at Baseline in addition to the categories of "low," "normal," "high" and "missing."

If there are multiple post-baseline measurements on the same day, the last value will be used.

Potentially Clinically Important Laboratory Values

Frequencies and percentages of subjects with post Baseline lab values meeting the following criteria in [Table 25](#) and [Table 26](#) will be summarized. Of note, a post baseline value must be more extreme than the baseline value to be considered a potentially clinically important finding.

Table 25. Criteria for Potentially Clinically Important Chemistry Values

Chemistry Variables	Units	Definition of Potentially Clinically Important Current (Version 4) NCI CTCAE Grade 3 or Greater	
		Very Low	Very High
TBL	mcmol/L		> 3.0 × ULN
SGOT/AST	U/L		> 5.0 × ULN
SGPT/ALT	U/L		> 5.0 × ULN
Albumin	g/L	< 20	
Glucose	mmol/L	< 2.2	> 13.9
Triglycerides	mmol/L		> 5.7
Creatinine	mcmol/L		> 3.0 × ULN
Sodium	mmol/L	< 130	> 155
Potassium	mmol/L	< 3.0	> 6.0
Calcium	mmol/L	< 1.75	> 3.1
CPK	U/L		> 5.0 × ULN
Total Cholesterol	mmol/L		> 10.34
GGT			> 5.0 × ULN
ALP			> 5.0 × ULN

Note: A post baseline value must be more extreme than the baseline value to be considered a potentially clinically important finding.

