11.4.2 Statistical Methods

Changes from Baseline to each visit and to the final value in vital sign parameters will be summarized with the mean, standard deviation and median. The Baseline and final value means will also be presented for subjects who have both the Baseline and final values (see Section 6.0 for the definition of Baseline and final values).

For baseline, if there are multiple measurements on the same day, the last measurement prior to the first dose of study drug will be used as the Baseline vital sign value. If there are multiple post-baseline measurements on the same day, average value will be used.

For systolic blood pressure, diastolic blood pressure and pulse, a listing of all subjects with any vital sign value meeting criteria for potentially clinically important values will be provided. For each of these subjects, the whole course of the respective parameter will be listed. The number and percentage of subjects who have at least one value meeting criteria for potentially clinically important values will be provided for each selected vital sign parameter.

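### Continuous safety variables are compared by one-way ANOVA without the baseline value; adding it would give a modest, nearly free gain in precision

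*SAP*

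**What the plan says.** SAP 11.1 sets the between-arm safety analysis: "Comparison between risankizumab group and placebo group will be performed in the Safety Population in Safety_A1 and Safety_B_R populations". The method is "Continuous variables will be analyzed using one-way ANOVA", with no covariate and no stratification factor. The section does not say whether the variable analysed is the change from baseline or the post-baseline value.

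The later sections describe changes. For laboratory data (SAP 11.3.2): "Changes from Baseline to each scheduled visit and to the final value in continuous laboratory parameters will be summarized". For vital signs (SAP 11.4.2): "Changes from Baseline to each visit and to the final value in vital sign parameters will be summarized". SAP 11.5 likewise gives mean changes from baseline for QTc.

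For continuous efficacy variables, SAP 10.1.2 takes the other route: "The treatment groups will be compared using ANCOVA with treatment group, Baseline value, and stratification factors in the model".

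Protocol 7.3.4 sets the status of all safety analyses: "In general, safety analyses will be descriptive in nature and will be based on AbbVie standards. No hypothesis testing is planned".

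**The concern.** With two arms, a one-way ANOVA is a two-sample t-test. Applied to a change score, it subtracts the whole baseline value from each patient's follow-up value, whatever the actual correlation. Unless that correlation is perfect, this over-corrects: patients with high baseline values tend to fall and those with low values tend to rise, and that predictable part stays in the error term. If the arms differ at baseline by chance, part of the difference also appears as a difference in change.

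At stake is the width of the interval around each mean difference in laboratory values, vital signs and QTc. The placebo arm in Part A1 is planned at only 100 patients, so precision there is worth having if it costs nothing. The SAP gives no reason for using a plainer model for safety than for efficacy.

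**Working it through.** **Inputs from the documents.** Part A1 is planned at 400:100 and the re-randomised comparison at 102:204 (protocol 7.7). The plan states no power or precision for any safety comparison, so there is no safety figure to reproduce. The sizes borrowed here do reproduce: 90% versus 75% at 1:2, two-sided 0.05 and 90% power gives 102 in the smaller arm (power 90.2%), and 306/0.8 = 382.5, rounded up to 383.

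**Assumptions.** rho is the correlation between baseline and follow-up and appears nowhere in the documents; 0.5 to 0.9 is used. The SD is the same at both times and set to 1.

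**Variance of the treatment difference**, with f = 1/n1 + 1/n2:

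- ANOVA on change: 2(1 − rho) × f
- ANCOVA: (1 − rho²) × f
- Ratio, ANCOVA to change: (1 + rho)/2

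At 400:100, f = 0.0025 + 0.0100 = 0.0125.

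| rho | SE, change | SE, ANCOVA | Variance ratio | Variance saved | Power of ANOVA on change where ANCOVA has 80% |
|---|---|---|---|---|---|
| 0.5 | 0.112 | 0.097 | 0.75 | 25% | 68% |
| 0.7 | 0.087 | 0.080 | 0.85 | 15% | 73% |
| 0.9 | 0.050 | 0.049 | 0.95 | 5% | 78% |

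A simulation at 400:100 (3,000 runs per value of rho) gave variance ratios of 0.76, 0.85 and 0.96. Both estimators had a mean difference of about zero, which confirms that neither is biased.

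The ratio is the same at 102:204 if change is measured from entry to Part B. At rho 0.7 the standard errors there are 0.094 and 0.087.

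**If the ANOVA is on post-baseline values**, its variance is f, and the ratio of ANCOVA to ANOVA is 1 − rho²: 0.75, 0.51 and 0.19 at rho 0.5, 0.7 and 0.9. ANCOVA is better on this reading too.

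**Unequal SDs.** With SD s0 at baseline and s1 at follow-up, the change-score variance minus the ANCOVA variance, per unit of f, is (s0² + s1² − 2 rho s0 s1) − s1²(1 − rho²) = (s0 − rho s1)². This is never negative, so in large samples ANCOVA does not lose.

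**Chance imbalance.** The standard error of a baseline mean difference at 400:100 is √0.0125 = 0.112 SD, so 5% of parameters are expected to differ by more than 1.96 × 0.112 = 0.22 SD. A change score carries over (1 − rho) of the imbalance. For 0.22 SD that is 0.11 SD at rho 0.5 (0.11/0.112, about one standard error of the estimate), 0.066 SD at 0.7 (about 0.76 of one) and 0.022 SD at 0.9 (0.022/0.050 = 0.44 of one).

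This is not a second loss. The excess variance of the change score is [2(1 − rho) − (1 − rho²)] × f = (1 − rho)² × f, which is exactly the variance of the carried-over imbalance. It is the same imprecision seen from the side of a single table.

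**The case against.** The best defence is that nothing here is wrong. The protocol calls safety analysis descriptive and plans no hypothesis test, so no decision rule rests on these means. A change score already uses the baseline value. The SAP also looks at shifts in ways that refer to each patient's own baseline: shift tables, potentially important values that must be more extreme than baseline, vital-sign criteria that require a set change, and categories of QTc change. All of this stands, and it is why the point is minor. It does not argue for omitting the covariate: the SAP plans the between-arm comparison anyway, and an adjusted difference with an interval serves a descriptive purpose at least as well as an ANOVA p-value.

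It also stands that SAP 11.1 does not name the variable analysed. The size of the gain depends on that; its direction does not.

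Three stronger readings are tempting, and the documents do not support them.

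- A reader might infer that Part A1 is the only placebo-controlled safety comparison. SAP 11.1 names Safety_B_R as well, planned with 204 placebo patients. Protocol 3.2 does say "Thus, only adverse events reported during the first 16 weeks of the trial can be directly compared to placebo", but that concerns adverse events, not laboratory values or vital signs. Safety_B_R is a weaker contrast, because its placebo patients have had risankizumab and its observations stop at retreatment, but it is a comparison with placebo.
- A reader might translate the gain into one third more patients. That is 1/0.75 = 1.33 and holds only at an assumed rho of 0.5; at 0.9 it is 1/0.95 = 1.05.
- A reader might call the result biased by regression to the mean. Under randomisation it is not. Chance imbalance affects a single realised table, and the ANOVA standard error already allows for it.

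**Conclusion.** The point holds as an optional gain in precision. It is neither an error nor a bias. Relative to ANOVA on change, baseline adjustment saves 25%, 15% and 5% of the variance at rho 0.5, 0.7 and 0.9, or about 13%, 8% and 2.5% of the standard error, and it removes the carry-over of chance baseline differences. The figures rest on an assumed rho, equal SDs and the reading that the ANOVA is on change. Parameters that are stable within a patient will gain little; noisier ones will gain more. Efficacy results, sample size and alpha are untouched.

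**What to change.** In SAP 11.1, replace the one-way ANOVA sentence for these variables with wording such as: *Change from baseline in continuous laboratory, vital-sign and QTc variables will be compared between arms in Safety_A1 and Safety_B_R by ANCOVA with treatment, the baseline value (for Safety_B_R, the value at entry to Part B) and the stratification factors. Adjusted differences will be presented with 95% confidence intervals as descriptive estimates.*

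This also states which variable is analysed, and it agrees with protocol 7.3.4. For Safety_B_R, say explicitly that change is measured from entry to Part B; the general definition of Baseline in SAP 6.0 leaves room for doubt.

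The cost is a sentence of SAP text and reuse of the model type already specified in SAP 10.1.2, with the Part B entry value as covariate for Safety_B_R. The rule that missing safety data are not imputed can stay. No new data are needed.

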7.7 DETERMINATION OF SAMPLE SIZE

This study is designed to show a difference between BI 655066 and placebo in terms of PASI90 response and sPGA scores of clear or almost clear at Week 16. However, this study was also powered to show a difference in sPGA response at Week 52 between the patients randomized to continue on BI 655066 vs. patients randomized to placebo at Week 28.

Based on the interim results from 1311.2 ([c03272682-01](#)), it is assumed at most 10% of the patients in the re-randomized BI 655066 arm will lose sPGA response of clear or almost clear (0 or 1) at Week 52 whereas approximately 25% of patients in the re-randomized placebo arm will lose response. Using a 1:2 re-randomisation scheme (BI 655066:placebo), 102 patients in the BI 655066 arm and 204 patients in the placebo arm will provide at least 90% power to detect the difference in sPGA response rate at Week 52. Assuming that 80% of patients on BI 655066 at baseline will achieve sPGA of clear or almost clear at Week 28, the total sample size required for the initial BI 655066 arm at Visit 2 is $(102)(3) \div 0.8 = 383$. See [Table 7.7:1](#) for more sample size calculations to have at least 90% power.

Table 7.7:1 Sample sizes for randomized withdrawal comparison

Response Rate at Week 52			Randomisation ratio at Week 28 active:placebo = Total N	Total N at randomisation
Active	Placebo	Delta	1:2	
90%	72.5%	17.5%	79:158 = 237	297
90%	75%	15%	102:204 = 306	383
90%	77.5%	12.5%	138:276 = 414	518

Calculated using ADDPLAN Version 6.0.4.

Thus 400 patients in the original BI 655066 arm, provide at least 90% power for the randomized withdrawal comparison. Using a 4:1 randomisation will yield a total sample size of 500 = 400:100 for BI 655066: placebo.

Based on the outcome from trials 1311.1 and 1311.2, the PASI90 response rate at Week 16 is assumed to be at least 65% in the BI 655066 arm and approximately 5% for placebo. For sPGA clear or almost clear at Week 16, the response rate for the BI 655066 arm is assumed to be at least 80% and approximately 5% for placebo. This trial will have >99% power for comparing each BI 655066 arm to placebo on both of these endpoints.

All calculations were performed using ADDPLAN Version 6.0.4, an Aptiv Solutions Company.

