4.2 Design Diagram

This is a confirmatory, multinational, multicenter, randomized, double-blind, placebo controlled study with randomized withdrawal and retreatment, evaluating the safety and efficacy of risankizumab 150 mg subcutaneous (SC) in patients with moderate to severe chronic plaque psoriasis.

The study consists of an up to 42 day screening period, a 16-week double-blind, placebo-controlled initial treatment period (Part A1), a 12-week treatment period (Part A2), an up to 60-week continuous treatment and treatment withdrawal period (Part B) with possible retreatment with risankizumab for up to 16 weeks, and a 16 week follow-up period.

Part A1: A 16-week double-blinded, placebo-controlled treatment period during which subjects will be randomized at a ratio of 4:1 to one of two treatment arms as shown in [Figure 1](#). Arm 1 refers to those subjects originally randomized to risankizumab and Arm 2 refers to those subjects originally randomized to placebo. The first dose of study drug will be administered on Day 1 (Visit 2; Baseline) and the second dose will be administered at Week 4. The randomization will be stratified with respect to weight (≤ 100 kg vs. > 100 kg) and prior exposure to TNF antagonists (0 vs. ≥ 1).

[figure not shown]
Part A2: A 12-week treatment period. At Week 16, all subjects will receive one dose of risankizumab 150 mg.

Part B: At Week 28, non-responders (static Physician Global Assessment [sPGA] ≥ 2) will receive open label risankizumab 150 mg every 12 weeks with a last dose at Week 88 (end-of-treatment, EOT), while responders (sPGA of 0 or 1) from Arm 1 will be

re-randomized in a 1:2 ratio to either maintain risankizumab 150 mg or matching placebo every 12 weeks with a last dose at Week 88 (EOT). The re-randomization will be stratified with respect to weight (≤ 100 kg vs. > 100 kg) and prior exposure to TNF antagonists (0 vs. ≥ 1). Responders from Arm 2 will continue to receive blinded risankizumab 150 mg every 12 weeks with a last dose at Week 88 (EOT) to maintain the blind. Throughout the SAP, "re-randomized" or "re-randomization" refers to the randomization at Week 28 among subjects from Arm 1 of Part A.

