4.3 Sample Size

This study is designed to show a difference between risankizumab and placebo in terms of achieving 90% reduction in Psoriasis Area and Severity Index (PASI 90) response and sPGA of clear or almost clear (sPGA of 0 or 1) at Week 16. This study was also powered to show a difference in sPGA response at Week 52 between the subjects re-randomized to continue on risankizumab vs. subjects randomized to placebo at Week 28.

Based on the interim results from Study 1311.2, it is assumed at most 10% of the subjects in the re-randomized risankizumab arm and approximately 25% of subjects in the re-randomized placebo arm will lose response. Using a 1:2 re-randomization scheme (risankizumab:placebo), 102 subjects in the risankizumab arm and 204 subjects in the

placebo arm will provide at least 90% power to detect the difference in sPGA response rate at Week 52. Assuming that 80% of subjects initially randomized to risankizumab at baseline will achieve sPGA of 0 or 1 at Week 28, the total sample size required for the initial risankizumab arm at Visit 2 is $(102)(3) \div 0.8 = 383$.

A total sample size of 500 = 400:100 for risankizumab: placebo was planned at Visit 2.

Based on the outcome from Trials 1311.1 and 1311.2, the PASI 90 response rate at Week 16 is assumed to be at least 65% in the risankizumab arm and approximately 5% for placebo. For sPGA clear or almost clear at Week 16, the response rate is assumed to be at least 80% for the risankizumab arm and approximately 5% for placebo. This trial will have > 99% power for comparing risankizumab arm to placebo on both of these endpoints.

All calculations were performed using ADDPLAN Version 6.0.4, an Aptiv Solutions Company.

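### SAP 11.1 adds Fisher tests for adverse events and prints only p-values up to 0.100, with no estimate or interval, although the protocol plans no safety testing

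*SAP*

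**What the plan says.** Protocol 7.3.4: "In general, safety analyses will be descriptive in nature and will be based on AbbVie standards". The next sentence is "No hypothesis testing is planned".

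SAP 11.1: "Comparison between risankizumab group and placebo group will be performed in the Safety Population in Safety_A1 and Safety_B_R populations". For the method, "categorical variables will be analyzed using Fisher's exact test", and for the display, "For analyses of AEs, only P values ≤ 0.100 when rounded to three digits will be presented". The sidedness of the safety tests is not stated. Neither SAP 11.1 nor 11.2 specifies a risk difference or confidence interval for AEs.

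SAP 14.1 lists four changes from the protocol: the population definitions, the separate Part B test hierarchy, the added Week 104 endpoint, and the Areas of Safety Interest. Safety testing is not among them. SAP 11.3.2, by contrast, states openly that its laboratory grading scale departs from the protocol.

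On arm sizes, SAP 4.2 says of Part A1 that "subjects will be randomized at a ratio of 4:1", and SAP 4.3 says "A total sample size of 500 = 400:100 for risankizumab: placebo was planned at Visit 2". Re-randomisation for Part B is 1:2, with 102 and 204 patients in Protocol 7.7.

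**The concern.** Two things stand out. The first is a conflict between the documents: the protocol excludes safety hypothesis tests, and the SAP adds them without recording the departure.

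The second is how the table will be read. When only some rows carry a p-value, the p-value becomes a flag and a blank can be taken for no difference. At 4:1 allocation that flag is far easier to trigger by a few placebo cases than by a similar percentage excess on risankizumab.

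Part A1 matters most here, because Protocol 3.2 says that only AEs in the first 16 weeks can be compared directly with placebo. The AE overview in SAP 11.2.1 includes deaths, adjudicated cardiovascular events, tuberculosis, serious infections and malignant tumours, which could plausibly be rare over 16 weeks.

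**Working it through.** **Inputs.** Part A1: 400 risankizumab, 100 placebo (SAP 4.3). Part B: 102 and 204 (Protocol 7.7). Rule: print if p, rounded to three digits, is at most 0.100 (SAP 11.1). Assumptions: two-sided Fisher test, and planned arm sizes standing in for the safety sets.

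The documents give no operating figure for this rule. The arm sizes do reproduce. A two-sided pooled test of 90% vs 75% at alpha 0.05, 90% power and ratio 1:2 gives 102:204, and 306 / 0.8 = 382.5, i.e. the stated 383, which the plan takes to 400.

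**Formula.** With k cases in total, P(x on risankizumab) = C(400, x) C(100, k − x) / C(500, k). The two-sided p sums all tables no more probable than the one observed.

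- k = 2, both on placebo: (100 × 99) / (500 × 499) = 0.040. The other two tables are more probable, so p = 0.040, **printed**.
- k = 12, all on risankizumab: this table has probability 0.066. Tables with 7 or fewer on risankizumab add 0.070, so p = 0.137, **blank**.
- k = 13, all on risankizumab: 0.053 + 0.028 = 0.081, **printed**.

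| Risankizumab | Placebo | p | Printed |
|---|---|---|---|
| 0/400 | 1/100 | 0.200 | no |
| 0/400 | 2/100 | 0.040 | yes |
| 8/400 | 0/100 | 0.367 | no |
| 12/400 | 0/100 | 0.137 | no |
| 13/400 | 0/100 | 0.081 | yes |

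The same 2-point difference is flagged in one direction (0/400 vs 2/100) and blank in the other (8/400 vs 0/100). The thresholds of 2 and 13 do not move at 407:100, 390:98 or 380:95.

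**Chance of a printed p-value in Part A1 when there is no true difference** (full enumeration of the two binomial counts):

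| True risk, both arms | Favours risankizumab | Against |
|---|---|---|
| 1% | 4.5% | 0.01% |
| 2% | 5.3% | 0.8% |
| 5% | 4.6% | 3.2% |

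With a true doubling on risankizumab (2% vs 1%), the excess is printed in 2.3% of trials. With a true halving (1% vs 2%), the benefit is printed in 20%.

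**Part B, 102:204.** The direction reverses: 3/102 vs 0/204 prints (p = 0.036), while placebo-only cases must reach 7/204 (p = 0.0999, which rounds to 0.100). With both risks at 1%, printing is 0.2% favouring risankizumab and 2.1% against.

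**What an interval would show.** For d = p1 − p2 with Wilson limits (l, u) for each arm, the Newcombe limits are d − √[(p1 − l1)² + (u2 − p2)²] and d + √[(u1 − p1)² + (p2 − l2)²]. For 12/400 vs 0/100, the Wilson limits are 1.72% to 5.17% and 0 to 3.70%:

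- lower limit: 3.0 − √(1.28² + 3.70²) = −0.9 points
- upper limit: 3.0 + 2.17 = +5.2 points

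For 0/400 vs 2/100 the interval is −7.0 to −0.3. With no placebo cases, the lower limit first passes zero at 17/400 (+0.2 to +6.7); at 16/400 it is still just below.

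**The case against.** A reader might infer that the 0.100 cutoff itself creates a bias towards risankizumab, or that it conceals harms. The documents support neither.

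- **The asymmetry is a property of exact inference at 4:1.** Under no effect, 12 cases are expected to split 9.6 to 2.4, and all 12 fall on risankizumab with probability 0.066. Two cases both fall on placebo with probability 0.040. The cutoff reports the weaker evidence as weaker. Printing every p-value, or showing intervals, leaves this unchanged: Newcombe excludes zero at 2 placebo-only cases but not before 17 risankizumab-only cases. This stands in full.
- **No AE is hidden.** SAP 11.2 tabulates counts and percentages whatever the p-value, with listings for serious events, deaths, discontinuations and Areas of Safety Interest, and rates per 100 patient-years. A reader of 12/400 vs 0/100 sees 3.0% against 0%. No safety conclusion depends on the cutoff. This also stands.
- **It is not a trial-wide tilt.** The rule covers Safety_B_R as well, where the direction reverses. In Part A1 the imbalance largely disappears by a 5% risk. The 2.3% figure is partly low power: equal arms of 250 would flag 2% vs 1% in only about 12% of trials.
- **Sponsor standards.** Protocol 7.3.4 is worded in general terms, refers to company standards and leaves detail to the SAP. That can excuse a display convention. It does not authorise tests that the following sentence excludes.

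What survives is the unrecorded departure from the protocol, and a selective flag with no estimate or interval beside it.

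**Conclusion.** The point holds as a conflict between the documents and a presentation weakness. It is a cheap improvement and does not threaten the trial's conclusions. SAP 11.1 adds AE tests that the protocol excludes, does not record this in SAP 14.1, and prints results selectively. For rare AEs in Part A1 the printed flags fall mostly on differences favouring risankizumab, because of the test and the allocation ratio. The consequence is limited to how the tables are read: a blank at 12/400 vs 0/100 says nothing of an interval that reaches +5.2 points.

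The figures assume a two-sided Fisher test and the planned arm sizes. A one-sided test or very different safety sets would change them.

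**What to change.** In SAP 11.1, drop the AE p-values and the 0.100 filter for both Safety_A1 and Safety_B_R. For every AE overview row and every system organ class and preferred term row, show counts, percentages and the risk difference with a 95% CI (Newcombe, for example), labelled descriptive as Protocol 7.3.4 intends. This puts the size and imprecision of the difference on every row and removes the selective flag.

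If AE p-values are kept, print all of them and list the departure from Protocol 7.3.4, with its reason, in SAP 14.1.

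The cost is a few sentences of SAP text and one column in the AE table shells. The downside is slightly wider tables.
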